APPENDIX 1 ADDITIONAL ETHICAL CONSIDERATIONS

1 INFORMED CONSENT PROCEDURES

BMS will provide the investigator with an appropriate (ie, Global or Local) sample informed consent form which will include all elements required by ICH, GCP and applicable regulatory requirements. The sample informed consent form will adhere to the ethical principles that have their origin in the Declaration of Helsinki.

The consent form must also include a statement that BMS and regulatory authorities have direct access to subject records. Prior to the beginning of the study, the investigator must have the IRB/IEC's written approval/favorable opinion of the written informed consent form and any other information to be provided to the subjects.

The investigator must provide the subject, or, in those situations where consent cannot be given by subjects, their legally acceptable representative with a copy of the consent form and written information about the study in the language in which the subject is most proficient. The language must be non-technical and easily understood. The investigator should allow time necessary for subject or subject's legally acceptable representative to inquire about the details of the study, then informed consent must be signed and personally dated by the subject or the subject's legally acceptable representative and by the person who conducted the informed consent discussion. The subject or legally acceptable representative should receive a copy of the signed informed consent and any other written information provided to study subjects prior to subject's participation in the study.

1.1 Subjects Unable to Give Written Informed Consent

1.1.1 *Minors*

For minors, according to local legislation, one or both parents or a legally acceptable representative must be informed of the study procedures and must sign the informed consent form approved for the study prior to clinical study participation. (In the event that the parents or legal guardians are unable to read, then an impartial witness should be present during the entire informed consent discussion). Whenever feasible, minors who are judged to be of an age of reason must also give their written assent by signing and dating the completed informed consent. All local laws, rules and regulations regarding informed consent of minors must be followed.

1.1.2 *Subjects Experiencing Acute Events or Emergencies*

A legally acceptable representative or legal guardian must provide informed consent when consent of the subject is not possible prior to clinical study participation, eg, for subjects experiencing an acute medical event such as myocardial infarction or stroke. Informed consent of the subject must additionally be obtained if they become capable of making and communicating their informed consent during the clinical study. All local laws, rules and regulations regarding informed consent of adult subjects incapable of giving informed consent must be followed.

1.1.3 *Mentally Impaired or Incapacitated Subjects*

Investigators (or whoever required by local regulations) should determine whether or not a mentally impaired or incapacitated subject is capable of giving informed consent and should sign a statement to that effect. If the subject is deemed mentally competent to give informed consent, the investigator should follow standard procedures. If the subject is deemed not to be mentally competent to give informed consent, a fully informed legal guardian or legally acceptable representative can be asked to give consent for, or on behalf of, the subject. All local laws, rules and regulations regarding informed consent of mentally impaired or incapacitated subjects must be followed.

Patients who are involuntarily hospitalized because of mental illness must not be enrolled in clinical studies

1.1.4 *Other Circumstances*

Subjects who are imprisoned or involuntarily detained for treatment of either a psychiatric or physical (eg, infectious disease) illness must not be enrolled in clinical studies.

In circumstances where a subject's only access to treatment is through enrollment in a clinical study, eg, for subjects in developing countries with limited resources or for subjects with no marketed treatment options, the investigator must take special care to explain the potential risks and benefits associated with the study and ensure that the subject is giving informed consent.

When a subject may be in a dependent relationship with the investigator, a well-informed physician who is not engaged in the clinical study and is completely independent of the relationship between the subject and investigator should obtain the subject's informed consent.

1.1.5 *Illiterate Subjects*

If the subject, or, in those situations where consent cannot be given by the subject, their legally acceptable representative is unable to read, a reliable and independent witness should be present during the entire informed consent discussion. The choice of the witness must not breach the subject's rights to confidentiality. A reliable independent witness is defined as one not affiliated with the institution or engaged in the investigation. A family member or acquaintance is an appropriate independent witness. After the subject or legally acceptable representative orally consents and has signed, if capable, the witness should sign and personally date the consent form attesting that the information is accurate and that the subject, or, in those situations where consent cannot be given by subjects, their legally acceptable representative has fully understood the content of the informed consent agreement and is giving true informed consent.

1.2 *Update of Informed Consent*

The informed consent and any other information provided to subjects, or, in those situations where consent cannot be given by subjects, the subject's legally acceptable representative, should be revised whenever important new information becomes available that is relevant to the subject's consent, and should receive IRB/IEC approval/favorable opinion prior to use. The investigator, or a person designated by the investigator should fully inform the subject or the

subject's legally acceptable representative of all pertinent aspects of the study and of any new information relevant to the subject's willingness to continue participation in the study. This communication should be documented.

During a subject's participation in the study, any updates to the consent form and any updates to the written information will be provided to the subject.

APPENDIX 2 PERFORMANCE STATUS SCALES

ECOG PERFORMANCE STATUS	
Grade	ECOG
0	Fully active, able to carry on all pre-disease performance without restriction
1	Restricted in physically strenuous activity but ambulatory and able to carry out work of a light or sedentary nature, eg, light house work, office work.
2	Ambulatory and capable of all self-care but unable to carry out any work activities. Up and about more than 50% of waking hours
3	Capable of only limited self-care, confined to bed or chair more than 50% of waking hours
4	Completely disabled. Cannot carry on any self-care. Totally confined to bed or chair
5	Dead

Source: Oken MM, Creech RH, Tomey DC, Horton J, Davis TE, McFadden ET, and Carbone PP. Toxicity and Response Criteria of the Eastern Cooperative Oncology Group. Am J Clin Oncol 1982; 5: 649-655.

APPENDIX 4 AJCC MELANOMA STAGING

Table 1. TNM Staging Categories for Cutaneous Melanoma

Classification	Thickness (mm)	Ulceration Status/Mitoses
T		
Tis	NA	NA
T1	≤ 1.00	a: Without ulceration and mitosis < 1/mm ² b: With ulceration or mitoses ≥ 1/mm ²
T2	1.01-2.00	a: Without ulceration b: With ulceration
T3	2.01-4.00	a: Without ulceration b: With ulceration
T4	> 4.00	a: Without ulceration b: With ulceration
N		
N	No. of Metastatic Nodes	Nodal Metastatic Burden
N0	0	NA
N1	1	a: Micrometastasis* b: Macrometastasis†
N2	2-3	a: Micrometastasis* b: Macrometastasis† c: In transit metastases/satellites without metastatic nodes
N3	4+ metastatic nodes, or matted nodes, or in transit metastases/satellites with metastatic nodes	
M		
M	Site	Serum LDH
M0	No distant metastases	NA
M1a	Distant skin, subcutaneous, or nodal metastases	Normal
M1b	Lung metastases	Normal
M1c	All other visceral metastases	Normal
	Any distant metastasis	Elevated

Abbreviations: NA, not applicable; LDH, lactate dehydrogenase.

*Micrometastases are diagnosed after sentinel lymph node biopsy.

†Macrometastases are defined as clinically detectable nodal metastases confirmed pathologically.

Table 2. Anatomic Stage Groupings for Cutaneous Melanoma

	Clinical Staging*			Pathologic Staging†			
	T	N	M	T	N	M	
0	Tis	N0	M0	0	Tis	N0	M0
IA	T1a	N0	M0	IA	T1a	N0	M0
IB	T1b	N0	M0	IB	T1b	N0	M0
	T2a	N0	M0		T2a	N0	M0
IIA	T2b	N0	M0	IIA	T2b	N0	M0
	T3a	N0	M0		T3a	N0	M0
IIB	T3b	N0	M0	IIB	T3b	N0	M0
	T4a	N0	M0		T4a	N0	M0
IIC	T4b	N0	M0	IIC	T4b	N0	M0
III	Any T	N > N0	M0	IIIA	T1-4a	N1a	M0
					T1-4a	N2a	M0
				IIIB	T1-4b	N1a	M0
					T1-4b	N2a	M0
					T1-4a	N1b	M0
					T1-4a	N2b	M0
					T1-4a	N2c	M0
				IIIC	T1-4b	N1b	M0
					T1-4b	N2b	M0
					T1-4b	N2c	M0
					Any T	N3	M0
IV	Any T	Any N	M1	IV	Any T	Any N	M1

*Clinical staging includes microstaging of the primary melanoma and clinical/radiologic evaluation for metastases. By convention, it should be used after complete excision of the primary melanoma with clinical assessment for regional and distant metastases.

†Pathologic staging includes microstaging of the primary melanoma and pathologic information about the regional lymph nodes after partial (ie, sentinel node biopsy) or complete lymphadenectomy. Pathologic stage 0 or stage IA patients are the exception; they do not require pathologic evaluation of their lymph nodes.

APPENDIX 5 METHODS OF CONTRACEPTION

At a minimum, subjects must agree to use one highly effective method of contraception as listed below:

HIGHLY EFFECTIVE METHODS OF CONTRACEPTION

Highly effective methods of contraception have a failure rate of < 1% when used consistently and correctly. WOCBP and female partners of male subjects, who are WOCBP, are expected to use one of the highly effective methods of contraception listed below. Male subjects must inform their female partners who are WOCBP of the contraceptive requirements of the protocol and are expected to adhere to using contraception with their partner. Contraception methods are as follows:

1. Progestogen only hormonal contraception associated with inhibition of ovulation.
2. Hormonal methods of contraception including oral contraceptive pills containing combined estrogen + progestrone, vaginal ring, injectables, implants and intrauterine devices (IUDs) such as Mirena®
3. Nonhormonal IUDs, such as ParaGard®
4. Bilateral tubal occlusion
5. Vasectomised partner with documented azoospermia 90 days after procedure
 - a) Vasectomised partner is a highly effective birth control method provided that partner is the sole sexual partner of the WOCBP trial participant and that the vasectomised partner has received medical assessment of the surgical success
6. Intrauterine hormone-releasing system (IUS)
7. Complete abstinence
 - a) Complete abstinence is defined as the complete avoidance of heterosexual intercourse. (refer to Glossary of Terms)
 - b) Complete abstinence is an acceptable form of contraception for all study drugs and must be used throughout the duration of the study treatment (plus 5 half-lives of the investigational drug plus 30 days)
 - c) It is not necessary to use any other method of contraception when complete abstinence is elected
 - d) Subjects who choose complete abstinence must continue to have pregnancy tests
 - e) Acceptable alternate methods of highly effective contraception must be discussed in the event that the subject chooses to forego complete abstinence
 - f) The reliability of sexual abstinence needs to be evaluated in relation to the duration of the clinical trial and the preferred and usual lifestyle of the subject

UNACCEPTABLE METHODS OF CONTRACEPTION

1. Periodic abstinence (calendar, symptothermal, post-ovulation methods)
2. Withdrawal (coitus interruptus)

3. Spermicide only
4. Lactation amenorrhea method (LAM)

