 - v) Serum creatinine $\leq 1.5 \times$ upper limit of normal (ULN) or calculated creatinine clearance $> 40 \text{ mL/min}$ (using the Cockcroft Gault formula):
$$\text{Female CrCl} = \frac{(140 - \text{age in years}) \times \text{weight in kg} \times 0.85}{72 \times \text{serum creatinine in mg/dL}}$$
$$\text{Male CrCl} = \frac{(140 - \text{age in years}) \times \text{weight in kg} \times 1.00}{72 \times \text{serum creatinine in mg/dL}}$$
 - vi) AST $\leq 3.0 \times$ ULN
 - vii) ALT $\leq 3.0 \times$ ULN
 - viii) Total Bilirubin $\leq 1.5 \times$ ULN (except subjects with Gilbert Syndrome who must have a total bilirubin level of $< 3.0 \times$ ULN)
- i) Subject Re-enrollment: This study permits the re-enrollment of a subject that has discontinued the study as a pre-treatment failure (ie, subject has not been randomized / has not been treated). If re-enrolled, the subject must be re-consented

3. Age and Reproductive Status

- a) Males and Females, ages ≥ 15 years of age
 - i) Except where local regulations and/or institutional policies do not allow for subjects < 18 years of age (pediatric population) to participate. For those sites, the eligible subject population is ≥ 18 years of age

- b) Women of childbearing potential (WOCBP) must have a negative serum or urine pregnancy test (minimum sensitivity 25 IU/L or equivalent units of HCG) within 24 hours prior to the start of study drug. Women must not be breastfeeding
- c) Women of childbearing potential (WOCBP) must agree to follow instructions for method(s) of contraception, as indicated in the informed consent form, for a period of 30 days (duration of ovulatory cycle) plus the time required for the investigational drug to undergo approximately five half-lives. WOCBP should therefore use an adequate method to avoid pregnancy for 5 months (30 days plus the time required for nivolumab to undergo approximately five half-lives) after the last dose of investigational drug (combination or monotherapy).

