- d) Males who are sexually active with WOCBP must agree to follow instructions for method(s) of contraception, as indicated in the informed consent form, for a period of 90 days plus the time required for the investigational drug to undergo approximately five half-lives. Men who are sexually active with WOCBP must continue contraception for 7 months (90 days plus the time required for nivolumab to undergo approximately five half-lives) after the last dose of investigational drug (combination or monotherapy). In addition, male subjects must be willing to refrain from sperm donation during this time.
- e) Azoospermic males are exempt from contraceptive requirements. WOCBP who are continuously not heterosexually active are also exempt from contraceptive requirements, and still must undergo pregnancy testing as described in this section.

Investigators shall counsel WOCBP, and male subjects who are sexually active with WOCBP, on the importance of pregnancy prevention and the implications of an unexpected pregnancy. Investigators shall advise on the use of highly effective methods of contraception ([Appendix 5](#)), which have a failure rate of < 1% when used consistently and correctly.

3.3.2 *Exclusion Criteria*

1. Target Disease Exceptions

- a) Active brain metastases or leptomeningeal metastases. Subjects with brain metastases are eligible if these have been treated and there is no magnetic resonance imaging (MRI - except where contraindicated in which CT scan is acceptable) evidence of progression for at least 8 weeks after treatment is complete and within 28 days prior to first dose of study drug administration. There must also be no requirement for high doses of systemic corticosteroids that could result in immunosuppression (> 10 mg/day prednisone equivalents) for at least 2 weeks prior to study drug administration.
- b) Ocular melanoma

2. Medical History and Concurrent Diseases

- a) Prior malignancy active within the previous 3 years except for locally curable cancers that have been apparently cured, such as basal or squamous cell skin cancer, superficial bladder cancer, or carcinoma in situ of the prostate, cervix, or breast
- b) Subjects with active, known or suspected autoimmune disease. Subjects with vitiligo, type I diabetes mellitus, residual hypothyroidism due to autoimmune condition only requiring

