10 GLOSSARY OF TERMS

Term	Definition
Complete Abstinence	Complete Abstinence is defined as complete avoidance of heterosexual intercourse and is an acceptable form of contraception for all study drugs. This also means that abstinence is the preferred and usual lifestyle of the patient. This does not mean periodic abstinence (eg, calendar, ovulation, symptothermal, profession of abstinence for entry into a clinical trial, post-ovulation methods) and withdrawal, which are not acceptable methods of contraception. Women must continue to have pregnancy tests. Acceptable alternate methods of highly or less effective contraception's must be discussed in the event that the subject chooses to forego complete abstinence.

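### Appendix 5 gives one post-treatment abstinence period for both sexes, 60 days shorter than the 7 months Section 3.3.1 sets for men, and the Glossary and Appendix 5 differ on which methods may replace abstinence

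*Protocol*

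**What the plan says.** **Duration.** Protocol Section 3.3.1 sets a separate period for each sex, counted from the last dose. For women of childbearing potential (WOCBP), 3(c) sets "5 months (30 days plus the time required for nivolumab to undergo approximately five half-lives"). For men sexually active with WOCBP, 3(d) says that they "must continue contraception for 7 months (90 days plus the time required for nivolumab to undergo approximately five half-lives"). Both criteria name the informed consent form as the source of instructions on methods. The paragraph after 3(e) tells investigators to advise highly effective methods, defined by a failure rate below 1%, and points to Appendix 5.

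The Appendix 5 list is not confined to female subjects: "WOCBP and female partners of male subjects, who are WOCBP, are expected to use one of the highly effective methods of contraception listed below". The appendix also tells men in the study to adhere to contraception with their partner. Item 7 of the list is complete abstinence, and item 7(b) gives a single period for it: it "must be used throughout the duration of the study treatment (plus 5 half-lives of the investigational drug plus 30 days").

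**Method.** Appendix 5 opens with a floor: "At a minimum, subjects must agree to use one highly effective method of contraception as listed below". Item 7(e) keeps to it: "Acceptable alternate methods of highly effective contraception must be discussed in the event that the subject chooses to forego complete abstinence". Item 7(a) sends the reader to the Glossary (Section 10), where the entry on complete abstinence closes with a near-identical sentence that has a wider scope: "Acceptable alternate methods of highly or less effective contraception's must be discussed in the event that the subject chooses to forego complete abstinence".

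**The concern.** Agreement to the contraception instructions is an entry condition, and its purpose is to prevent fetal exposure to study drug. Sites and consent forms therefore need one end date for each sex and one standard of method.

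On duration, a man who elects abstinence finds one end point in item 7(b) and a later one in 3(d). If he takes the first as the end of his obligation and resumes unprotected intercourse with a WOCBP, he is inside the period that 3(d) covers.

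On method, a site that follows the reference from item 7(a) to the Glossary meets a class of alternatives that item 7(e) leaves out and that no part of the protocol text supplied defines.

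**Working it through.** **1. Does Section 3.3.1 agree with itself?** Inputs are 5 months and 30 days from 3(c), and 7 months and 90 days from 3(d). The SAP's conversion (Section 8) of 30.4375 days per month is borrowed for the arithmetic only. Solving each rule for five half-lives:

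- Women: 5 x 30.4375 - 30 = 152.2 - 30 = 122.2 days, or 24.4 days per half-life.
- Men: 7 x 30.4375 - 90 = 213.1 - 90 = 123.1 days, or 24.6 days per half-life.
- With 30-day months, both give 120 days, or 24.0 days per half-life.

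The stated 5 and 7 months therefore rest on the same five half-lives, and the two criteria are consistent with each other.

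**2. Where does item 7(b) end?** Taking the same five half-lives and the same starting point (end of treatment, read as the last dose):

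| Rule | Formula | 30.4375-day months | 30-day months |
|---|---|---|---|
| 3.3.1, 3(c), women | 5 half-lives + 30 d | 152 d | 150 d |
| Appendix 5, 7(b), no split by sex | 5 half-lives + 30 d | 152 to 153 d | 150 d |
| 3.3.1, 3(d), men | 5 half-lives + 90 d | 213 d | 210 d |

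Item 7(b) has the same formula as the women's rule. Against the men's rule, the gap is (5h + 90) - (5h + 30) = 60 days. The half-life h cancels, so any value gives 60 days. Counted as two calendar months, the gap is 2 x 30.4375 = 60.9 days.

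**3. How much rests on the half-life being the same?** Item 7(b) refers to the investigational drug, and the 7-month figure is tied to nivolumab. The documents supplied give no half-life for any product. If h(N) is the half-life behind 3(d) and h(A) the one meant in item 7(b), the gap is 60 + 5 x [h(N) - h(A)]. With h(N) = 24.6 days from step 1, and an assumed range for h(A):

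- h(A) = 15 days: 60 + 5 x 9.6 = 108 days.
- h(A) = 24.6 days: 60 days.
- h(A) = 30 days: 60 - 5 x 5.4 = 33 days.
- The gap would close only at h(A) = 24.6 + 12 = 36.6 days.

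Section 3.3.1 supports the equal-half-life reading: 3(c) and 3(d) each state the rule first for the investigational drug and then give its length in months using nivolumab.

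**4. Who is affected?** Criterion 3(d) addresses men who are sexually active with WOCBP.

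- Abstinent for the full 7 months: meets both texts.
- Resumes after the item 7(b) period and uses a listed method up to 7 months: meets both texts.
- Resumes without contraception between about 5 and 7 months: meets item 7(b), but not 3(d).

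Only the third man is caught by the conflict. The documents give no basis for estimating how many there would be.

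**5. Method standard, side by side.** The Appendix 5 opening and item 7(e) name highly effective methods only. The Glossary sentence adds less effective ones. Appendix 5 has two lists, one of highly effective methods and one of unacceptable methods, and no list of acceptable less effective methods. The wider Glossary wording therefore has no defined content.

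**The case against.** The strongest reply is that item 7(b) was written as the women's rule. Its formula is that of 3(c), which links the 30 days to the ovulatory cycle. Item 7(d) requires continued pregnancy tests, and the parallel Glossary sentence attaches those tests to women. The male period is stated plainly in 3(d), and item 7(b) says how long abstinence must last as a method, without saying that the 3(d) period is over. On the Glossary, the sentence says only that alternatives must be discussed, and a phrase in a definition does not displace the minimum at the head of Appendix 5.

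Much of this explains how the texts came to differ, but it does not remove the difference. Item 7(b) is not limited to women, it stands in a list that also covers male subjects and their partners, and Appendix 5 gives no separate period for men. The Glossary sentence is reached by a direct reference from item 7(a) and contradicts item 7(e) in almost the same words.

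The reply does limit the consequences. A reader might infer more than the documents support:

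- *That every man electing abstinence is released 60 days early.* Criterion 3(d) binds only men sexually active with WOCBP, so the exposed group is the third case in step 4.
- *That 3(d) itself points to Appendix 5, or that the criteria list the permitted methods.* Criteria 3(c) and 3(d) cite the consent form and list no methods. The reference to Appendix 5 is in the paragraph after 3(e), on what investigators advise.
- *That an affected subject becomes ineligible.* The criterion is agreement at entry. Later conduct is a matter of compliance on study and does not undo eligibility.
- *That subjects are in fact given conflicting instructions.* The consent pages were not part of the material reviewed, so this cannot be settled here.

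**Conclusion.** Both inconsistencies stand in the current protocol text. Item 7(b) of Appendix 5 agrees with Section 3.3.1 for women and is 60 days shorter than Section 3.3.1 for men (about 153 against 213 days). That figure assumes the same half-life in both passages and a common starting point at the last dose. Its practical reach is narrow: men who elect abstinence and resume unprotected intercourse with a WOCBP between about 5 and 7 months after treatment. The Glossary and Appendix 5 also give different standards for what may replace abstinence, and the wider one is undefined.

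The point deserves correction because it bears on fetal safety and is simple to resolve. It has no bearing on any endpoint, sample size or analysis. Nothing here judges which period or which method standard is right.

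**What to change.** - Reconcile Appendix 5 item 7(b) with Section 3.3.1, 3(c) and 3(d), so that each sex has one stated post-treatment period.
- Reconcile the last sentence of the Glossary entry on complete abstinence with Appendix 5 item 7(e), so that the protocol has one method standard.
- Check that the consent form, which 3(c) and 3(d) name as the source of instructions, carries the same text.

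The sponsor's clinical team decides which text stands in each case. The cost is about two sentences in the protocol, matching consent wording where needed, and the ethics committee review that Section 9.1.1 attaches to protocol changes. Statistical methods, data collection and the analysis plan stay as they are.
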